10.5.5 Population-level Summary

The population-level summary for the primary endpoint is the difference in primary variable means between each atogepant group and placebo.

Participants are always analyzed based on their treatment assignment by randomization. To obtain the estimate of treatment effect defined in the off-treatment hypothetical estimand, an MMRM similar to the primary analysis specified in Section 10.2.1 will be performed on observed data collected from both double-blind treatment period and follow-up period. The model terms include treatment group, visit (derived as month), prior exposure (yes/no) to a migraine prevention medication with proven efficacy, treatment- by-visit interaction, the baseline score and baseline-by-visit interaction.

10.5.6 Off-treatment Hypothetical Estimand Approach for the Secondary Endpoints

Continuous secondary endpoints based on eDiary data will be handled using the same estimand approach defined above for the primary endpoint.

The secondary endpoint of 50% responders are derived at least a 50% reduction from baseline in the 3-month average of monthly migraine days using data collected from the double-blind period and follow-up period. Data after participants started a new prophylaxis treatment during the follow-up period will be excluded. The population-level summary for this endpoint is the odds ratio from a logistic regression for each atogepant group relative to placebo with baseline monthly migraine days as a covariate, prior exposure (yes/no) to a migraine prevention medication with proven efficacy and treatment group as fixed factors.

The graphical approach to control the overall Type I error rate described in Section 10.3 will be provided for primary and key secondary endpoints in the analysis population for off-treatment hypothetical estimand.

11 Safety Analyses

The safety analysis will be performed using the Safety Population. The safety parameters will include adverse events (AEs), clinical laboratory, vital sign, electrocardiographic (ECG), and C-SSRS. For clinical laboratory, vital sign, and ECG, the last non-missing safety assessment before the first dose of treatment will be used as the baseline for all analyses of that safety parameter. Continuous variables will be summarized by number of participants and mean, SD, median, Q1, Q3, minimum, and maximum values. Categorical variables will be summarized by number and percentage of participants.

11.1 Adverse Events

Adverse events will be coded by system organ class and preferred term using the Medical Dictionary for Regulatory Activities (MedDRA), version 22.0 or newer.

An AE will be considered as a treatment-emergent adverse event (TEAE) if the AE began or worsened (increased in severity or became serious) on or after the date of the first dose of double-blind study treatment. An AE that occurs more than 30 days after the last dose of double-blind study treatment or Visit 8 whichever comes later will not be counted as a TEAE. Per case report form instructions, a new AE record will be created for any AE that worsens; therefore, TEAEs can be identified as those AEs captured in Study 3101-301-002 with recorded onset date on or after the date of the first dose of double-blind study treatment and within 30 days after the last dose of double-blind study treatment or Visit 8 whichever comes later. An AE will be considered as a treatment-emergent SAE (TESAE) if it is a TEAE that also meets SAE criteria. TEAEs that started after the date of last dose of study treatment will be considered as newly emergent.

Only AEs captured in Study 3101-301-002 will be considered for TEAEs in this study. For participants rolling over into Study 3101-309-002 (extension study) who start the first dose on Visit 1 or beyond, AEs captured in Study 3101-309-002 will be summarized in that study although some AEs might occur within 30 days after the last dose from Study 3101-301-002.

Overall summary of AEs will be provided on a per-participant basis for categories of TEAEs, treatment-related TEAEs, deaths, TESAEs, and TEAEs leading to treatment discontinuation.

The number and percentage of participants reporting TEAEs in each treatment group will be tabulated by system organ class and preferred term, and further categorized by severity to the study treatment.

SAP 3101-301-002 AGN-241689

The number and percentage of participants reporting treatment-related TEAEs in each treatment group will be tabulated by system organ class and preferred term.

The number and percentage of participants reporting newly emergent TEAEs in each treatment group will be tabulated by system organ class and preferred term.

The number and percentage of participants who have TEAEs leading to treatment discontinuation will be summarized by system organ class, preferred term and treatment group.

The incidence of common ($\geq 2\%$ of participants in any treatment group) TEAEs will be summarized by preferred term, and treatment group. A similar 5% table will be provided as well.

The number and percentage of participants who have TESAE in each treatment group will be tabulated by system organ class and preferred term.

In addition, separate tabular displays will be presented for patients who died, participants with SAEs, and participants with TEAEs leading to treatment discontinuation.

11.2 Clinical Laboratory Assessments

Descriptive statistics for clinical laboratory values (in SI units) at baseline, postbaseline, and changes from baseline values at each postbaseline timepoint will be presented by treatment group for the following laboratory parameters:

Hematology: Hemoglobin, hematocrit, red blood cell count, red blood cell

indices (mean corpuscular volume, mean corpuscular hemoglobin, mean corpuscular hemoglobin concentration), white blood cell count, including differential (neutrophils, lymphocytes, monocytes, eosinophils, and basophils),

platelet count

Chemistry: Sodium, potassium, chloride, bicarbonate, glucose, blood

urea nitrogen, creatinine, total bilirubin, alkaline phosphatase, aspartate aminotransferase, alanine

aminotransferase, lactate dehydrogenase, creatine kinase, total protein, albumin, calcium, phosphorus, uric acid, total

cholesterol, eGFR

Urinalysis: Specific gravity, pH

In addition, descriptive statistics for values and changes from the baseline values in conventional units at each assessment time point will be presented for selected clinical laboratory parameters

SAP 3101-301-002 AGN-241689

listed in Appendix I. A description of reporting the lab values in conventional units in patient narratives (along with the standard reporting in SI units) is presented at the end of Appendix I.

Clinical laboratory test values will be considered potentially clinically significant (PCS) if they meet either the lower-limit or higher-limit PCS criteria listed in Table 11–1. The normal range for eGFR was not collected in the lab. Therefore, eGFR<60 mL/min/1.73m² is defined in Table 11–2 to classify renal function as the category of "Moderate eGFR Decrease or Worse" based on FDA guidance on PK studies in Patients with impaired renal function. The number and percentage of participants who have PCS postbaseline clinical laboratory values will be tabulated by treatment group. The percentages will be calculated relative to the number of participants with available non-PCS baseline values and at least 1 postbaseline assessment for the double-blind treatment period. The numerator will be the total number of participants with available non-PCS baseline values and at least 1 PCS postbaseline value during the study. A supportive tabular display of participants with PCS postbaseline values will be provided, including the PID number, baseline and all postbaseline (including non-PCS) values.

In addition, a tabular display showing all AEs that occurred in participants who had PCS postbaseline clinical laboratory values will be provided.

Shift tables from baseline to end of the double-blind treatment period for clinical laboratory parameters will be presented by treatment group for the following categories: low, normal, and high, which are provided by the laboratory vendor.

Potential Hy's Law criteria within a 24-hour window is defined by a post baseline elevation of alanine aminotransferase (ALT) or aspartate aminotransferase (AST) ≥ 3 x ULN, along with total bilirubin (TBL) ≥ 2 x ULN and a non-elevated alkaline phosphatase (ALP) < 2 x ULN, all based on blood draws collected within a 24-hour period. Potential Hy's Law criteria without time window is defined by maximum of post baseline elevation of ALT or AST ≥ 3 x ULN, along with maximum of post baseline elevation of TBL ≥ 2 x ULN. Patients who meet the potential Hy's Law criteria from the first dose of study drug to the end of study will be summarized. Supportive tabular displays will also be provided.

Table 11–1 Criteria for Potentially Clinically Significant Laboratory Values

			PCS (Criteria
Category	Parameter	SI Unit	PCS Low	PCS High
Chemistry	Albumin	g/L	< 0.8 × LLN	> 1.2 × ULN
	Alanine aminotransferase	U/L		\geq 3.0 × ULN
	Alkaline phosphatase	U/L	_	\geq 3.0 × ULN
	Aspartate aminotransferase	U/L	_	\geq 3.0 × ULN
	Bicarbonate	mmol/L	< 0.9 × LLN	> 1.1 × ULN
	Bilirubin, total	μmol/L	_	$\geq 1.5 \times ULN$
	Blood urea nitrogen	mmol/L		> 1.5 × ULN
	Calcium	mmol/L	< 0.9 × LLN	> 1.1 × ULN

SAP 3101-301-002 AGN-241689

Table 11–1 Criteria for Potentially Clinically Significant Laboratory Values

			Criteria
Parameter	SI Unit	PCS Low	PCS High
Chloride	mmol/L	$< 0.9 \times LLN$	> 1.1 × ULN
Cholesterol, total	mmol/L		> 1.6 × ULN
Creatinine	μmol/L		> 1.5 × ULN
Creatine kinase	U/L		> 2.0 × ULN
Estimated glomerular filtration rate	$mL/min/1.73m^2$	< 60	_
Glucose, nonfasting	mmol/L	$< 0.8 \times LLN$	> 2.0 × ULN
Lactate dehydrogenase (LDH)	U/L		> 3.0 × ULN
Phosphorus	mmol/L	$< 0.9 \times LLN$	> 1.1 × ULN
Potassium	mmol/L	$< 0.9 \times LLN$	> 1.1 × ULN
Protein, total	g/L	$< 0.9 \times LLN$	> 1.1 × ULN
Sodium	mmol/L	$< 0.9 \times LLN$	> 1.1 × ULN
Triglycerides	mmol/L		> 2.0 × ULN
	μmol/L		> 1.2 × ULN
Basophils, absolute cell count			> 2.0 × ULN
Eosinophils, absolute cell count			> 2.0 × ULN
Hematocrit	Ratio	$< 0.9 \times LLN$	> 1.1 × ULN
Hemoglobin	g/L	$< 0.9 \times LLN$	> 1.1 × ULN
Lymphocytes, absolute cell count		$< 0.7 \times LLN$	> 1.3 × ULN
Monocytes, absolute cell count		$< 0.5 \times LLN$	> 2.0 × ULN
Neutrophils, absolute cell count		$< 0.7 \times LLN$	> 1.3 × ULN
Platelet count		$< 0.5 \times LLN$	> 1.5 × ULN
Red blood cell count		< 0.9 × LLN	> 1.1 × ULN
White blood cell count	$10^{9}/L$	< 0.9 × LLN	> 1.5 × ULN
рН	рН	< 0.9 × LLN	> 1.1 × ULN
Glucose	_		At least 1+
Protein	_		At least 1+
Specific gravity			> 1.1 × ULN
	Chloride Cholesterol, total Creatinine Creatine kinase Estimated glomerular filtration rate Glucose, nonfasting Lactate dehydrogenase (LDH) Phosphorus Potassium Protein, total Sodium Triglycerides Uric acid Basophils, absolute cell count Eosinophils, absolute cell count Hematocrit Hemoglobin Lymphocytes, absolute cell count Neutrophils, absolute cell count Platelet count Red blood cell count White blood cell count pH Glucose Protein	Chloride mmol/L Cholesterol, total mmol/L Creatinine upmol/L Creatine kinase U/L Estimated glomerular filtration rate mL/min/1.73m² Glucose, nonfasting mmol/L Lactate dehydrogenase (LDH) U/L Phosphorus mmol/L Potassium mmol/L Protein, total g/L Sodium mmol/L Triglycerides mmol/L Uric acid upmol/L Basophils, absolute cell count 10°/L Eosinophils, absolute cell count 10°/L Hematocrit Ratio Hemoglobin g/L Lymphocytes, absolute cell count 10°/L Neutrophils, absolute cell count 10°/L Neutrophils absolute cell count 10°/L Platelet count 10°/L Red blood cell count 10°/L Phyle Blood cell count 10°/L Phyle Glucose —— Protein ——	Parameter SI Unit PCS Low Chloride mmol/L < 0.9 × LLN

LLN = lower limit of normal value; ULN = upper limit of normal value; normal value provided by laboratory.

The number and percentage of participants meeting each of the following criteria for postbaseline hepatic laboratory abnormalities listed in Table 11–2 will be summarized by treatment group. The percentages will be calculated relative to the number of participants with at least 1 available postbaseline assessment. The numerator will be the total number of participants having at least 1 postbaseline value that meets the specific category during the study. A supportive listing will also be provided.

SI = Le Système International d'Unités (International System of Units).

eGFR<60 mL/min/1.73m² indicates moderate eGFR decrease or worse.

Table 11-2 Criteria for Hepatic Laboratory Abnormalities

Laboratory Parameter	Categories
	≥ 1 × ULN
	≥ 1.5 × ULN
	$\geq 2 \times ULN$
ALT	\geq 3 × ULN
	≥ 5 × ULN
	≥ 10 × ULN
	\geq 20 × ULN
	$\geq 1 \times \text{ULN}$
	≥ 1.5 × ULN
	$\geq 2 \times ULN$
AST	\geq 3 × ULN
	≥ 5 × ULN
	≥ 10 × ULN
	≥ 20 × ULN
	≥ 1 × ULN
	≥ 1.5 × ULN
	\geq 2 × ULN
ALT or AST	≥ 3 × ULN
	≥ 5 × ULN
	≥ 10 × ULN
	\geq 20 × ULN
	$\geq 1 \times \text{ULN}$
	≥ 1.5 × ULN
	$\geq 2 \times \text{ULN}$
Bilirubin Total	\geq 3 × ULN
	\geq 5 × ULN
	$\geq 10 \times \text{ULN}$
	$\geq 20 \times \text{ULN}$
	$\geq 1 \times \text{ULN}$
	≥ 1.5 × ULN
	\geq 2 × ULN
Alkaline Phosphatase	\geq 3 × ULN
	≥ 5 × ULN
	≥ 10 × ULN
	≥ 20 × ULN
Concurrent Elevations ¹	ALT or AST \geq 3 × ULN and Bilirubin Total \geq 1.5 × ULN
	ALT or AST $>= 3 \times ULN$ and Bilirubin Total $\geq 2 \times ULN$
Potential Hy's Law ¹	ALT or AST \geq 3 × ULN and Bilirubin Total \geq 2 × ULN and ALP $<$ 2 × ULN
	•

ALT = alanine aminotransferase; AST = aspartate aminotransferase; TBL = total bilirubin; ALP = alkaline phosphatase; ULN = upper limit of normal (value provided by the laboratory).

¹ Elevations are from the same day

[figure not shown]
The number and percentage of participants with an adjudicated case (i.e., $ALT \ge 3 \times ULN$) and/or $AST \ge 3 \times ULN$) will be summarized by treatment group and by relationship of ALT or AST elevation to study medication. The percentages will be calculated relative to the number of participants with at least 1 adjudicated case. The numerator will be the number of participants with at least 1 adjudicated case in the specific category of relationship. If a participant has more than 1 adjudicated case, he or she will be counted in the most relevant category of relationship.

Participants with an adjudicated case (i.e. $ALT \ge 3 \times ULN$ or $AST \ge 3 \times ULN$) will be listed with their ALT and AST assessments, adjudication dates, relationship of ALT or AST elevation to study medication, and confounding factor(s). Additional listings will be provided for participants who meet $ALT \ge 3 \times ULN$ or $AST \ge 3 \times ULN$ and/or potential Hy's law and have one of the following categories: at least 1 abnormal liver biochemistry risk factor, at least 1 liver disease sign and symptom, at least 1 liver diagnostic test performed, consultation with a specialist for liver evaluation, liver lab tests performed, and drug screen performed, respectively. A listing of urine pregnancy test results will be provided for female participants of child-bearing potential with at least one positive result.

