## 8.8 Early Discontinuation of Participants

A premature discontinuation will occur when a participant who signed the ICF and has been randomized ceases participation in the study, regardless of circumstances, before completion of the study. Participants can be prematurely discontinued from the study for one of the following reasons:

- AE
- Lack of efficacy
- Lost to follow-up
- Non-compliance with study intervention
- Other
- Pregnancy
- Protocol deviation
- Site terminated by Allergan
- Study terminated by Allergan
- Withdrawal by participant

Participants may voluntarily withdraw from the study at any time. Notification of early participant discontinuation from the study and the reason for discontinuation will be made to Allergan and will be documented on the appropriate case report form. All randomized participants who prematurely discontinue from the study, regardless of cause, should be seen for final study assessments. The final assessments will be defined as completion of the evaluations scheduled for Visit 7/ET and Visit 8 Follow-up, 4 weeks post the last dose of study intervention. These participants must continue to complete their eDiary through Visit 8 Follow-up.

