11.3 Vital Signs

Descriptive statistics for vital signs (systolic and diastolic blood pressures [sitting and standing], pulse rate [sitting and standing], respiratory rate, temperature, weight, orthostatic systolic blood pressure, orthostatic diastolic blood pressure, and orthostatic pulse rate) values at baseline, postbaseline, and changes from baseline values at each postbaseline timepoint will be presented by treatment group. Orthostatic vital sign values (orthostatic systolic and diastolic blood pressures, and orthostatic pulse rate) are defined as the corresponding standing measurement minus sitting measurement of systolic and diastolic blood pressures and pulse rate respectively.

Vital sign values will be considered PCS if they meet both the observed value criterion and the change from baseline value criterion, if both criteria are available, or meet either the observed value criterion or the change from baseline value criterion that will be detailed in Table 11–3. The number and percentage of participants who have PCS postbaseline vital sign values will be tabulated by treatment group. For criteria related with systolic blood pressure, diastolic blood pressure, pulse rate and weight, the denominator will be the number of participants who have available baseline and at least 1 postbaseline assessment. For criteria related with orthostatic measures, the denominator will be the number of participants who have available non-PCS baseline and at least 1 postbaseline assessment. The numerator will be the total number of participants with at least 1 PCS postbaseline value during the study. A supportive listing of participants with PCS postbaseline values will be provided. In addition, a tabular display

showing all AEs that occurred in participants who had PCS postbaseline vital sign values will be provided.

Table 11–3 Criteria for Potentially Clinically Significant Vital Signs

D	Flag	Criteria		
Parameter		Observed Value	Change from Baseline	
C -4-1'-111	High	≥ 180	Increase of ≥ 20	
Systolic blood pressure, mm Hg	Low	≤ 90	Decrease of ≥ 20	
Disease 11 - 11 - 1	High	≥ 105	Increase of ≥ 15	
Diastolic blood pressure, mm Hg	Low	≤ 50	Decrease of ≥ 15	
D. I	High	≥ 120	Increase of ≥ 15	
Pulse rate, bpm	Low	≤ 50	Decrease of ≥ 15	
W.J.L. L.	High		Increase of ≥ 7%	
Weight, kg	Low	_	Decrease of ≥ 7%	
Orthostatic SBP change, mm Hg	Low	≤ -20	_	
Orthostatic DBP change, mm Hg	Low	≤ -15	_	
Orthostatic Pulse rate change, bpm	High	≥ 25	_	

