11.4 Electrocardiograms

Allergan

Descriptive statistics for ECG parameters (i.e., heart rate, PR interval, QRS interval, RR interval, QT interval, and QTc interval) at baseline, postbaseline, and changes from baseline values at each postbaseline timepoint will be presented by treatment group.

ECG parameter values are considered PCS if ECG values meet either the actual value or change from baseline PCS high criteria listed in Table 11-4. The number and percentage of participants with PCS postbaseline values will be tabulated by study treatment. The percentages will be calculated relative to the number of participants with an available non-PCS baseline value and at least 1 postbaseline assessment. The numerator will be the total number of participants with an available non-PCS baseline value and at least 1 PCS postbaseline ECG value during the study. A supportive listing of participants with PCS postbaseline values will be provided. A listing of all AEs for participants with PCS ECG values will also be provided.

Table 11-4 Criteria for Potentially Clinically Significant Electrocardiograms

Parameter	Unit	Criterion
QRS interval	msec	≥ 150
PR interval	msec	≥ 250
QTc (QTcB or QTcF) interval	msec	> 500
QTc (QTcB or QTcF) interval	msec	Increase from baseline > 60

QTc = QT interval corrected for heart rate.

To evaluate ECG postbaseline values of clinical interest, the number and percentage of participants with post-treatment QTcF > 450 msec, > 480 msec, and > 500 msec will be tabulated by treatment group.

The number and percentage of participants with an increase > 30 msec but \le 60 msec, and with an increase > 60 msec in QTcF will be tabulated. Participants will be counted only once for the most severe category. A supportive listing of participants with postbaseline QTcF increases > 30 msec will be provided, including the PID number, study center, and all QTc values (including changes from baseline). A listing of all AEs for participants with postbaseline QTcF increases > 30 msec will also be provided.

A shift table from baseline to the end of double-blind treatment period in the investigator's overall interpretation of the ECG will be presented by treatment group for the following categories: normal; abnormal, not clinically significant; abnormal, clinically significant. A tabular display of participants with postbaseline clinically significant ECG abnormalities according to the investigator's overall interpretation will be provided.

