17.3 Repeated or Unscheduled Assessments of Safety Parameters

Baseline is defined as the last assessment made before the first dose of double-blind study treatment. If a participant has 2 or more visits within the same window, the last visit with a nonmissing value will be used for summary over time unless specified otherwise. If end-of-study assessments are repeated or if unscheduled visits occur, the last non-missing postbaseline assessment will be used as the end-of-study assessment for generating summary statistics. However, all postbaseline assessments will be used for PCS value determinations, and all assessments will be presented in the data listings.

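### Two PCS safety percentages (orthostatic vital signs in SAP 11.3, laboratory values in SAP 11.2) can count participants in the numerator who are not in the denominator

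*SAP*

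**What the plan says.** **Orthostatic criteria (SAP 11.3).** For the orthostatic measures, "the denominator will be the number of participants who have available non-PCS baseline and at least 1 postbaseline assessment". The next sentence serves all vital signs: "The numerator will be the total number of participants with at least 1 PCS postbaseline value during the study". It has no baseline condition. In Table 11-3 the three orthostatic rows are judged on the observed value alone, with no change-from-baseline criterion.

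**Laboratory values (SAP 11.2).** The denominator is participants with "available non-PCS baseline values and at least 1 postbaseline assessment for the double-blind treatment period". The numerator is participants with "available non-PCS baseline values and at least 1 PCS postbaseline value during the study". The study includes a 4-week follow-up after the 12-week double-blind period (SAP Section 4), so the two windows differ.

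**Sibling rules.** For the hepatic abnormalities in Table 11-2, SAP 11.2 says: "The percentages will be calculated relative to the number of participants with at least 1 available postbaseline assessment", with no period limit. The ECG rule in SAP 11.4 also has no period limit in its denominator, and its numerator is participants with an "available non-PCS baseline value and at least 1 PCS postbaseline ECG value during the study". The laboratory and ECG rules both repeat the non-PCS baseline in the numerator. The hepatic, vital sign and ECG rules all count over the whole study without limiting the denominator to the double-blind period.

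**The concern.** A percentage whose numerator can include people outside its denominator is not a proportion of any defined group. The orthostatic rule also mixes two things. A non-PCS baseline in the denominator signals a rate of newly emergent abnormality, but the numerator as worded lets in participants who already had the abnormality before dosing. The laboratory rule mixes two observation windows.

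Each rule can be repaired in more than one way, and the choice of repair changes the printed figure, so the SAP should make it. These are descriptive tables: no hypothesis test, alpha allocation or sample size figure is involved.

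**Working it through.** The plan prints no figure for this point, so there is nothing to reproduce. The check has two parts: which participants break the subset relation, and how much that could matter under stated assumptions.

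**1. Who is counted in the numerator but not the denominator?** All combinations of baseline status, assessment and PCS value were enumerated against the wording.

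- Orthostatic rule, two types: (a) PCS at baseline and PCS postbaseline; (b) no baseline available and PCS postbaseline. Type (b) arises because the orthostatic criteria need only an observed value. The blood pressure, pulse and weight rows all use a change from baseline, so the gap matters only for the orthostatic rows.
- Laboratory rule, one type: non-PCS baseline, no double-blind postbaseline assessment, and a PCS value after the double-blind period.

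**2. Orthostatic size.** Take participants with a baseline and at least one postbaseline assessment. Let b be the share who are PCS at baseline, q the chance that such a participant is PCS again later, and p the true rate among those not PCS at baseline. As written, the percentage is

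[p(1 − b) + qb] / (1 − b) = p + qb/(1 − b),

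so the inflation is qb/(1 − b). The documents give neither b nor q, so these values are assumptions:

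- b = 1%, q = 30%: 0.003/0.99 = 0.30 points
- b = 2%, q = 50%: 0.010/0.98 = 1.02 points
- b = 5%, q = 70%: 0.035/0.95 = 3.68 points

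Type (b) participants would add to this and are not included. Taking q = 20% to 50% over the same range of b gives 0.2 to 2.6 points, so the range reflects the assumptions rather than the trial.

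**3. Orthostatic effect on the contrast between arms.** Suppose the true rates are 4.0% vs 2.0% (ratio 2.00).

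- b = 2%, q = 50% in both arms: 5.02% vs 3.02%, ratio 1.66.
- b = 2% in both arms, q = 70% vs 30%: the additions are 0.014/0.98 = 1.43 and 0.006/0.98 = 0.61 points, giving 5.43% vs 2.61%, ratio 2.08.

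The ratio can move either way.

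**4. Laboratory size.** Let n participants per arm have a non-PCS baseline and any postbaseline value, k of them have no double-blind value, and r be the PCS risk, equal in both groups. As written the percentage is rn/(n − k). Aligned on the whole study it is r. The inflation is rk/(n − k). With n = 218 (planned arm size, SAP Section 15) and k and r assumed:

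- r = 2%: k = 1 gives 0.02 × 1/217 = 0.009 points; k = 10 gives 0.02 × 10/208 = 0.096 points
- r = 10%: k = 1 gives 0.046 points; k = 10 gives 0.481 points

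With 227 per arm (910 randomised, SAP 18.1, divided by 4 and rounded down) the corresponding values are 0.009, 0.092, 0.044 and 0.461.

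**5. Choice of laboratory repair.** Assume 218 in an arm, 4 with a double-blind PCS value, and 1 with no double-blind value but a PCS value in follow-up.

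- As written: 5/217 = 2.30%
- Whole study in both parts: 5/218 = 2.29%
- Double-blind period in both parts: 4/217 = 1.84%

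Both repairs leave no participant outside the denominator.

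**The case against.** **The laboratory case may be nearly empty.** It needs someone with no double-blind laboratory result at all. Early discontinuers are asked for "completion of the evaluations scheduled for Visit 7/ET and Visit 8 Follow-up" (Protocol 8.8), and Protocol 8.4.2 places Visit 7/ET within the double-blind phase. Rollover participants need no Visit 8 (Protocol Section 3), and Visit 8 is remote during the pandemic (Protocol 8.4.3.1). The visit and window tables are not shown in the public copy, so a scheduled Visit 8 draw cannot be confirmed. Unscheduled tests (Protocol 6.5.3) keep the case possible. This stands as a limit on size, and k = 10 per arm is hard to believe.

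**A programmer would draw the numerator from the denominator anyway.** That is a natural reading of SAP 11.3. However, the laboratory and ECG rules repeat the baseline condition in the numerator, so its absence here is not a house convention. SAP Section 4 refers table specifications to a separate document, which may settle the matter. The wording fault is therefore established, but an effect on the printed tables is not.

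**Stronger readings that the documents do not support.**

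- A reader might infer that the orthostatic gap pulls the ratio between arms towards 1. That holds only if the added amount is similar in both arms, which nothing in the documents establishes.
- A reader might take SAP 17.3, under which "all postbaseline assessments will be used for PCS value determinations", as ruling out a double-blind restriction for laboratory values. That sentence sits under repeated and unscheduled assessments and contrasts with using the last value in a window. It is compatible with a whole-study window but does not decide between the two windows. The laboratory and ECG shift tables do stop at the end of double-blind treatment.
- A reader might extend the point to the adjudicated ALT/AST percentages in SAP 11.2. There the numerator is a subset of the stated denominator (participants with an adjudicated case), so there is no error of this kind.

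**Conclusion.** The point holds, as a minor error in wording. Followed literally, each rule can count participants outside its own denominator. The orthostatic gap is the easier one to reach, because it needs only a participant who is PCS on an observed value before and after dosing. It inflates the percentage and mixes pre-existing with new abnormalities. The documents do not allow the amount to be estimated, and the 0.3 to 3.7 points rest wholly on the assumed b and q.

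The laboratory mismatch is probably very small. Even under the generous assumption of 10 affected participants per arm and a 10% PCS risk it stays below half a point. The effect on comparisons between arms has no predictable direction. Efficacy conclusions and error control are untouched.

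**What to change.** - **SAP 11.3:** for the orthostatic criteria, add to the numerator sentence the condition of an available non-PCS baseline, as the laboratory and ECG rules already do. This removes both types of participant found above.
- **SAP 11.2:** use the same window in both parts of the PCS laboratory rule. The preferred edit is to delete the words that tie the denominator to the double-blind period, which matches the windows of the hepatic, vital sign and ECG rules. Limiting both parts to the double-blind period would also be coherent, provided the SAP says so.

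The cost is one phrase added and one deleted, with the table specifications checked to agree. No new data are needed, no planned display is lost, and no efficacy analysis changes.
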